9.7.4 Duplex ultrasound

Color duplex ultrasound measurements shall be used to determine stenosis percentage and location, either during the visit itself or within 30 days prior of the patient visit. Duplex shall be acquired from all limbs enrolled in the study with PAD/CLI as defined via the definitions in Section 8.4. If duplex ultrasound is not available, X-ray angiography will be considered a suitable alternative for calculation of stenosis and location. Color duplex ultrasound imaging will be performed in a similar fashion as the study by Lewis, et al. [30]. First, the distal common femoral artery (CFA) will be imaged and the Doppler waveform (DW) assessed visually for any loss of triphasic flow due to significant iliac disease. If the DW shows indications of this, then the iliac arteries will be assessed for the presence of atherosclerotic disease. The scan will continue distally from the CFA assessing the superficial femoral artery (SFA), popliteal, anterior tibial, posterior tibial, and peroneal arteries in the longitudinal plane. The extent and severity of any arterial disease are assessed by measuring the peak systolic velocity (PSV) from the DW just proximal to and distal through the stenosis. For each measured artery, if perceptible stenosis exists, the location of maximum stenosis will be identified and PSV values distal and proximal to the arterial stenosis will be noted on the CRF. The shape of the waveform (i.e. monophasic, biphasic, or triphasic) measured distal to the stenosis shall also be noted. If no stenosis is noted, this will be indicated on the CRF.

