Subjects enrolled in the Healthy cohort will be assessed according to Event Schedule C in the CIP at a single time point. Imaging outside standard of care will not be performed on the healthy subjects, and healthy cohort subjects with normal ABI and TBI values will be assumed not to have significant peripheral arterial stenosis.

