5.6 Exclusion Criteria

Candidates for this study who meet any of the following criteria at the time of the baseline visit are not eligible to be enrolled in this study:

PAD Positive Cohort Exclusion

- Subject is under 40 or unable to consent.
- Subject has any medical condition, which, in the judgment of the Investigator and/or designee, makes the subject a poor candidate for the investigational study.
- Subject is excluded from analysis if no stenosis is found during Doppler but Tibial disease is suspected and Tibial ultrasound is not able to be performed.
- Subject does not have a suitable finger to attach the FlowMet-R probe.
- Subject does not have a suitable 1st or 2nd digit to attach FlowMet-R probe on the limb of interest.
- Subject has undergone revascularization within the last 90 days
- Subject cannot lay safely in a supine position.

Healthy Cohort Exclusion

- Subject is under 40 or unable to consent.
- Subject has any medical condition, which, in the judgment of the Investigator and/or designee, makes the subject a poor candidate for the investigational study.
- One or more limbs has a prior or current diagnosis of PAD, or is reasonably suspected of having a diagnosis of PAD.
- Subject does not have a suitable finger to attach the FlowMet-R probe.
- Subject does not have a suitable 1st or 2nd digit to attach FlowMet-R probe.
- Subject has undergone revascularization within the last 90 days

6. Determination of Sample Size

The rate of PAD and CLI within the population seen at a typical vascular clinic is estimated from a prior investigation. In that study, 100 limbs were assessed using the ABI and graded using the Rutherford classification scheme. PAD (diagnosed via ABI score of <0.9) was present in 63% of limbs. CLI (estimated as having a Rutherford category of ≥ 4) occurred in 15% of limbs. FlowMet-R data was also collected from the above limbs, and the data analysis techniques used in the data analysis section below were applied to build a diagnostic model for PAD and CLI. ROC curves were then generated for the diagnosis of both Claudication and CLI. The resulting area under the curve (AUC) for these ROC curves was 0.67 and 0.80, respectively. However, the Claudicant group AUC had a tighter confidence interval due to larger sample size (84 vs. 22, respectively).

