7.1.3 Analysis Sets

Full Analysis Set

The full analysis set will include all participants and be used for all analyses. Visits outside of visit windows will be assigned to the nearest window. If a participant is missing data for a specific analysis, they will be excluded for that analysis. Within the analysis set, the grouping participants into the healthy, PAD (definitions 1 and 2), and CLI groups are defined in section 4.1.1.1.

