7.4 Handling of Missing, Unused, and Spurious Data and Dropouts

Data that is missing or incomplete will not be imputed. Complete case data will be used where all data for the respective analysis is available for a patient or visit.

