7.10.2 Secondary Objectives

The secondary endpoints will be analyzed as follows:

1. The capability of the acceleration time from the FlowMet-R device to predict a vascular intervention or amputation will occur within three and six months following initial visit will be determined using the AUC from an ROC curve where the endpoint is vascular intervention or amputation within 7 months, which is the end of the 6 month follow-up window. The 95% CI of the AUC will be derived using the method described in DeLong, et al (1998) [15].
2. The capability of the acceleration time from the FlowMet-R device to predict a $\geq 50\%$ stenosis determined using the AUC from an ROC curve where the endpoint is vascular intervention or amputation within 7 months, which is the end of the 6 month follow-up window. The 95% CI of the AUC will be derived using the method described in DeLong, et al (1998) [15].
3. The correlations between the acceleration time from the FlowMet-R device and peripheral artery stenosis, changes in ABI, and changes in TBI will be computed using Pearson correlations. The changes for ABI and TBI will be as follows: 0 to 3 months, 0 to 6 months, and 3 to 6 months.
4. The correlation between the acceleration time from the FlowMet-R device and changes in Rutherford Classification will be computed using the Spearman correlation. The changes for Rutherford Classification will be as follows: 0 to 3 months, 0 to 6 months, and 3 to 6 months.

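### The SAP does not say whether un-imaged healthy limbs count as stenosis-free in the stenosis analyses, and sections 5.6 and 7.1.3 conflict over limbs with unseen tibial disease

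*SAP*

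**What the plan says.** **Healthy limbs.** SAP section 5 (Investigation Plan), like Protocol section 5 (Study Design), states: "Imaging outside standard of care will not be performed on the healthy subjects". It adds that "healthy cohort subjects with normal ABI and TBI values will be assumed not to have significant peripheral arterial stenosis". Protocol 9.7.4 requires duplex, or angiography in its place, only for diseased limbs: "Duplex shall be acquired from all limbs enrolled in the study with PAD/CLI".

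**Who is analysed.** SAP 7.1.3 says: "The full analysis set will include all participants and be used for all analyses". The same section adds: "If a participant is missing data for a specific analysis, they will be excluded for that analysis". Section 7.2 also leaves missing values out, and 7.4 says: "Data that is missing or incomplete will not be imputed".

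**Unseen tibial disease.** SAP 5.6 (and Protocol 8.4) contains: "Subject is excluded from analysis if no stenosis is found during Doppler but Tibial disease is suspected", where tibial ultrasound cannot be done. The definition of the full analysis set does not repeat this.

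**The stenosis analyses.** SAP 4.1.2.1 lists an ROC curve for stenosis above 50% and a correlation with the greatest percent stenosis. SAP 7.10.2 names no limb population for either. Item 2 of 7.10.2 describes "stenosis determined using the AUC from an ROC curve where the endpoint is vascular intervention or amputation within 7 months", so as written the outcome of the stenosis ROC is not stenosis.

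**The concern.** PAD and CLI are defined from ABI, TBI and symptoms. Stenosis status is an outcome only in the two stenosis endpoints of 4.1.2.1, so the natural use of the healthy-limb assumption is to supply negatives there. If it is used that way, about 160 limbs with no image join the comparison as negatives. Any difference in acceleration time between PAD and healthy limbs then raises the stenosis AUC, even if the device cannot separate stenosed from non-stenosed limbs among those imaged.

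The status of those limbs is also weakly supported. Protocol 3.1 puts the sensitivity of ABI for stenosis above 50% at roughly 15% to 79%, so a normal ABI does not rule stenosis out.

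The tibial conflict is a separate matter. If these limbs are kept, they may be recorded as having no stenosis when the suspected artery was never seen. If the subjects are removed from everything, they also leave the primary ROC, which rests on ABI, TBI and symptoms and needs no imaging.

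**Working it through.** The plan states no sample size, power or expected AUC for the stenosis analyses, so there is no figure to reproduce. The check asks what each reading would produce.

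**Inputs from the documents**
- 160 control limbs and 240 PAD limbs (SAP section 6).
- Pilot AUCs of 0.67 (claudication) and 0.80 (CLI), with a lower planning value of 0.67 − 0.05 = 0.62 (SAP section 6).

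**Assumptions, not in the documents**
- All 240 PAD limbs are imaged, and m = 60 of them have no significant stenosis. The share is varied below.
- Among imaged limbs the device is unrelated to stenosis (AUC 0.50).
- A, the PAD-versus-healthy AUC, is 0.62, 0.67, 0.725 or 0.80. The value 0.725 is intermediate, close to the pilot values weighted by 140 non-CLI and 100 CLI limbs: (140 × 0.67 + 100 × 0.80)/240 = 0.724.
- Limbs are independent.

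**Step 1: stenosis AUC if healthy limbs count as negatives.** A stenosed limb beats an imaged negative with probability 0.5 and a healthy limb with probability A, so

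AUC = (160 × A + m × 0.5)/(160 + m).

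With m = 60:

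| A | Calculation | Stenosis AUC |
|---|---|---|
| 0.62 | (99.2 + 30)/220 | 0.587 |
| 0.67 | (107.2 + 30)/220 | 0.624 |
| 0.725 | (116 + 30)/220 | 0.664 |
| 0.80 | (128 + 30)/220 | 0.718 |

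Under the complete-case reading, the expected value is 0.50 in every row.

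**Step 2: vary the share of PAD limbs with significant stenosis from 50% to 90%** (m = 120 down to 24).
- A = 0.67: from (107.2 + 60)/280 = 0.597 to (107.2 + 12)/184 = 0.648.
- A = 0.80: from (128 + 60)/280 = 0.671 to (128 + 12)/184 = 0.761.

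With Hanley–McNeil standard errors, the 95% interval would exclude 0.5 with probability 0.87 to 1.00 across these cases. Among imaged limbs only, the interval is 0.50 ± 0.073 (50% share) to ± 0.122 (90% share).

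**Step 3: correlation, only if healthy limbs are coded 0%.** The SAP assigns no percent value to these limbs, so this step is conditional. The simulation used 2,000 runs, with percent stenosis in PAD limbs assumed at mean (SD) 50 (30), 60 (25) or 75 (20), clipped to 0–100, and no association within PAD. Pearson r averaged 0.22 to 0.27 for A = 0.67 and 0.38 to 0.47 for A = 0.80, with p < 0.05 in at least 99% of runs. With PAD limbs only, r was about 0 and p < 0.05 in about 5% of runs.

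**Step 4: limbs with unseen tibial disease, if kept and labelled negative.** Take u such limbs as truly stenosed and typical of stenosed limbs, with 60 true negatives and a true stenosis AUC of B among imaged limbs:

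AUC = (60 × B + u × 0.5)/(60 + u).

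- B = 0.67: u = 5, 10, 20 gives 42.7/65 = 0.657, 45.2/70 = 0.646, 50.2/80 = 0.628.
- B = 0.80: u = 5, 10, 20 gives 50.5/65 = 0.777, 53/70 = 0.757, 58/80 = 0.725.

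This error lowers the AUC, so it runs opposite to Step 1. The values of u are assumed.

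**The case against.** **The complete-case rules point the other way.** A reader might infer that the SAP plans to count healthy limbs as stenosis-free. It does not say so. Section 5 can be read as explaining why healthy subjects are not imaged, and under 7.1.3, 7.2 and 7.4 a limb with no image has missing stenosis data and drops out. This stands as a legitimate reading. It does not settle the matter, because an assumed status can equally be treated as non-missing, and 7.10.2 does not choose.

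**The assumption is binary.** It says no significant stenosis, not 0%. An inflated correlation therefore cannot be presented as a consequence of the SAP.

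**A whole-population association may be real.** If healthy limbs truly lack stenosis, an AUC over all limbs is a valid quantity, and neither document restricts the question to PAD limbs. That is correct, but the quantity depends on the recruited mix of 160 and 240 and on unverified status. It does not show whether the device tracks stenosis among limbs where stenosis was measured. The ABI sensitivity range does not give the number of missed stenoses either, since the rule also requires a normal TBI.

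**The tibial limbs are not un-imaged and are not called stenosis-free.** They had Doppler, 5.6 excludes them, and its heading speaks of candidates not eligible for enrolment, so some may never enter the full analysis set. A reader might add them to the healthy-limb problem as a second source of false association. The documents do not support that: no text labels them negative, and a wrong label would weaken the association. What remains is the conflict with 7.1.3. It is not idle. Protocol 9.7.4 has the absence of stenosis noted on the case report form, and Protocol 12.1.3 may classify a limb by its worst artery, so a negative label is possible.

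**The consequence is limited.** These are secondary endpoints, and 7.2 calls the results descriptive. That reduces the weight of the point, but an AUC with a 95% interval will still be read as evidence about detecting stenosis.

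**Conclusion.** The plan leaves open which limbs enter the stenosis ROC and correlation, and the two readings give materially different answers. With no association among imaged limbs, applying the healthy-limb assumption would give a stenosis AUC of about 0.59 to 0.72 (60 imaged negatives, PAD-versus-healthy AUC 0.62 to 0.80), against 0.50 with complete cases. The size depends on the assumed share of stenosed limbs and on the PAD-versus-healthy AUC; the upward direction needs only a PAD-versus-healthy AUC above 0.5. Inflation of the correlation holds only if healthy limbs are coded 0%.

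The conflict between 5.6 and 7.1.3 is real and separate. One resolution may bias the stenosis AUC downward; the other removes usable limbs from the primary analysis.

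The documents do not support saying that the SAP manufactures a stenosis association. They support saying that it permits one and should state its choice before the data are seen. The change should be made, at the weight appropriate to a secondary endpoint.

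**What to change.** Change the SAP wording as follows:
- **7.10.2, population:** base the main stenosis ROC and correlation on limbs with complete duplex or angiographic imaging. Show the version with assumed-free healthy limbs beside it as a labelled sensitivity analysis.
- **7.10.2, unseen tibial disease:** set stenosis to missing when tibial disease is suspected but not imaged.
- **5.6 and 7.1.3:** reconcile them so that this exclusion applies to the stenosis analyses only and the limbs stay in the primary ROC.
- **7.10.2 item 2:** make stenosis the endpoint of the stenosis ROC, as in 4.1.2.1. Without this, the population rule would govern an ROC with the wrong outcome.

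No extra imaging or data collection is needed. The cost is fewer limbs, a wider interval and probably a smaller stenosis AUC or correlation. For example, with 70% of PAD limbs stenosed and no association among them, the 95% half-width is about 0.080 in imaged limbs only, against about 0.056 with the 160 healthy limbs added (interval 0.561 to 0.673 at a PAD-versus-healthy AUC of 0.67).

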5.1 Duration

The expected study duration is approximately 24-36 months. The duration of individual subject participation will vary based on timing of their enrollment and completion of the final follow-up visit; however, at a minimum, participation of an individual subject will be at least 6 months for subjects suspected of having PAD and 0 months for healthy subjects.

5.2 Rationale

The study will assess the FlowMet-R's ability to provide a simple and continuous method of assessing PAD severity. To achieve the objectives defined in Section 4.1, FlowMet-R measurements will be acquired from the limbs of enrolled patients and the relationship between the FlowMet-R data and positive diagnosis of PAD and CLI will be evaluated at multiple time points (initial measurement, 3 month follow up, and 6 month follow up). Resulting sensitivity, specificity, accuracy, and ROC curves will be generated to demonstrate diagnostic capability. Changes in FlowMet-R data for enrolled patients at each study time point will be compared to corresponding changes in ABI, TBI, or patient symptoms. Finally, the prognostic capability of FlowMet-R data will be assessed by calculating the sensitivity and specificity of predicting whether surgical (re)intervention will be necessary following initial assessment.

5.3 Study Population

Subjects shall be enrolled until the following number of limbs have been measured:

- 160 control limbs (no diagnosed PAD)
- 240 limbs with PAD
 - Of the limbs with PAD, a subset >100 limbs with CLI
 - Of the limbs with PAD, a subset >54 limbs without CLI

Any patient being seen for diagnosis of suspected PAD may be screened for enrollment in the PAD cohort. For patients undergoing intervention, supplemental data will be taken within a catheterization laboratory. Control data from a healthy cohort will also be gathered. Recruitment of healthy subjects is at the site's discretion. Third party recruitment services such as researchmatch.org may be used.

5.4 Subject Enrollment

First, the patient will be asked if he/she would like to participate in the study. If so, they will undergo the informed consent procedure.

When a subject and the principal investigator or authorized designee, as required, have personally signed and dated the IC, the subject is considered to be enrolled in the study. The date the subject signed the IC must be documented in the subject's medical records.

Subjects will be screened to ensure they meet all of the inclusion and none of the exclusion criteria prior to study enrollment.

5.5 Inclusion Criteria

Candidates for this study must meet all of the following inclusion criteria:

PAD Positive Cohort

- Subject meets PAD positive criteria set forth in Section 4.1.1.1
- Subject is willing and able to provide an informed consent.
- Subject is willing and able to comply with the study procedures.
- Subject is able to understand the study procedures.
- Subject is scheduled for vascular examination that includes noninvasive assessments as standard of care: ABI, TBI, and either a Duplex ultrasound or Angiogram.

Healthy Cohort

- Subject is willing and able to provide an informed consent.
- Subject is willing and able to comply with the study procedures.
- Subject is able to understand the study procedures.
- Subject has no history of positive PAD diagnosis and is not currently suspected of having PAD.

5.6 Exclusion Criteria

Candidates for this study who meet any of the following criteria at the time of the baseline visit are not eligible to be enrolled in this study:

PAD Positive Cohort Exclusion

- Subject is under 40 or unable to consent.
- Subject has any medical condition, which, in the judgment of the Investigator and/or designee, makes the subject a poor candidate for the investigational study.
- Subject is excluded from analysis if no stenosis is found during Doppler but Tibial disease is suspected and Tibial ultrasound is not able to be performed.
- Subject does not have a suitable finger to attach the FlowMet-R probe.
- Subject does not have a suitable 1st or 2nd digit to attach FlowMet-R probe on the limb of interest.
- Subject has undergone revascularization within the last 90 days
- Subject cannot lay safely in a supine position.

Healthy Cohort Exclusion

- Subject is under 40 or unable to consent.
- Subject has any medical condition, which, in the judgment of the Investigator and/or designee, makes the subject a poor candidate for the investigational study.
- One or more limbs has a prior or current diagnosis of PAD, or is reasonably suspected of having a diagnosis of PAD.
- Subject does not have a suitable finger to attach the FlowMet-R probe.
- Subject does not have a suitable 1st or 2nd digit to attach FlowMet-R probe.
- Subject has undergone revascularization within the last 90 days

6. Determination of Sample Size

The rate of PAD and CLI within the population seen at a typical vascular clinic is estimated from a prior investigation. In that study, 100 limbs were assessed using the ABI and graded using the Rutherford classification scheme. PAD (diagnosed via ABI score of <0.9) was present in 63% of limbs. CLI (estimated as having a Rutherford category of ≥ 4) occurred in 15% of limbs. FlowMet-R data was also collected from the above limbs, and the data analysis techniques used in the data analysis section below were applied to build a diagnostic model for PAD and CLI. ROC curves were then generated for the diagnosis of both Claudication and CLI. The resulting area under the curve (AUC) for these ROC curves was 0.67 and 0.80, respectively. However, the Claudicant group AUC had a tighter confidence interval due to larger sample size (84 vs. 22, respectively).

Using a conservative estimation that the AUC for distinguishing PAD groups from healthy controls remains within $+/ - 0.05$ of the Claudicant group, and $+/ - 0.2$ of the CLI group, an estimate for the necessary sampling size can be determined. A standard type I error rate (α) of 0.05 and power of 0.8 is desired, thus the following approximate sample size was calculated [13,14]: 160 control limbs and 240 limbs with PAD, of which at least 54 limbs with Claudication and at least 100 limbs with CLI. Limbs with CLI may be included as a subset of limbs with PAD. A minimum of 250 patients (400 limbs) and maximum of 400 patients will be enrolled in the study.

7. Statistical Methods

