12.1.2 FlowMet-R data analysis and diagnostic model

FlowMet-R data is comprised of continuous blood flow data recorded over 30 seconds. Over this time, a pulsatile blood flow waveform may be present due to the subject's cardiac cycle, provided that digital blood flow is sufficient to generate such a signal. Thus, a combination of the flow amplitude and one or more features of the waveform may be used as inputs to train the predictive model.

The target outcome variable for training the model shall be a continuous metric of PAD severity, analogous to the ABI or TBI. The training will be performed as a regression using iterative algorithms ubiquitous in machine learning.

The predicted outputs from the regression model will be used to generate an ROC curve by classifying a binary diagnostic (i.e. PAD true/false, CLI true/false), or prognostic (i.e. vascular intervention likely within 6 months (true/false)). The classification algorithm which results in the highest diagnostic area under the curve for PAD and CLI shall be chosen to compute final sensitivity and specificity.

A k-fold cross validation scheme will be implemented to gauge model generalization. k-fold cross validation is a statistical sampling method that can be used to train and objectively validate the above

classification algorithms [34]. Using this scheme, only a subset of the total body of collected data is used to train the model, which is then applied to the remaining data withheld from training prospectively. During this validation stage, the performance and generalizability of the model can be assessed. Cross validation allows more objective selection of the optimal algorithm because performance assessment is based upon applying the model to a data set which it is naïve to (i.e. a prospective application of the model).

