7.2 General Methodology

Data analysis will be performed by Medtronic employed statisticians/programmers. All statistical analyses will be generated using SAS version 9.4 or later or R version 4.1 or later software. Demographic and baseline characteristics will be summarized descriptively and will include age, gender, ethnicity, race, body mass index and hemodynamic measures (ABI, TBI, and acceleration time from the FlowMet-R device). For continuous variables, descriptive statistics will be presented including the number of

subjects with the measurement, mean, standard deviation, median, minimum and maximum. For categorical variables, descriptive statistics will include the number with the characteristic, the number evaluated, and the percentage.

Subject enrollment and accountability, visit attendance, and end of study status will be displayed using a STROBE like diagram and descriptive statistics, as appropriate. For each study visit, the following information will be tallied: completed visits, missed visits, deaths (if any), study withdrawals, and lost to follow-up. Compliance with study visits will be summarized as the percent of subjects available at each visit.

Missing data for endpoints may result from clinical assessments that were unable to be performed or data missing from the FlowMet device. These missing values will be excluded from summaries and analyses. In general, efforts will be made to minimize missing data and imputation of missing data will not be performed.

The objectives are not hypothesis-driven and therefore their results will be presented descriptively with no adjustments for multiple comparisons.

The value from the predictive model from the FlowMet-R measurements will be derived by the Research and Development team and will consist of the acceleration time.

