7.10 Evaluation of Objectives

7.10.1 Primary Objectives

The primary objectives will compare the 95% CI of the AUC from the ROC curve to a value of 0.5 at 0-, 3-, and 6-months for the two definitions of PAD and one definition of CLI using the acceleration time from the FlowMet-R device. The 95% CI will not be corrected for repeated measures within a participant. If the 95% CI of the AUC excludes 0.5 at all time points for PAD or CLI, the acceleration time from the FlowMet-R device will be considered predictive of the respective endpoint. The 95% CI of the AUC will be derived using the method described in DeLong, et al (1998) [15]. Note, the definition of PAD will be defined two ways and analyzed separately. Definitions of PAD and CLI are provided in Section 4.1.1.1.1.

Three supplementary summaries will be computed. The sensitivity and specificity will be computed by selecting the point on the ROC curve closest to the upper left corner. Accuracy will be computed as the number of limbs correctly diagnosed divided by the total number of limbs.

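### The stated power of 0.8 rests on pilot AUCs for another set of disease definitions and apparently another predictor, and the ±0.05 allowance called conservative is less than half the pilot's own 95% half-width

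*SAP*

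**What the plan says.** SAP section 6 takes its inputs from one earlier study of 100 limbs, in which 63% had PAD (ABI below 0.9) and 15% had CLI (Rutherford category 4 or higher). In that study "the data analysis techniques used in the data analysis section below were applied to build a diagnostic model for PAD and CLI". For claudication and CLI in turn, "The resulting area under the curve (AUC) for these ROC curves was 0.67 and 0.80, respectively". The SAP adds that "the Claudicant group AUC had a tighter confidence interval due to larger sample size (84 vs. 22, respectively".

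The planning assumption follows: "Using a conservative estimation that the AUC for distinguishing PAD groups from healthy controls remains within" ±0.05 of the claudication value and ±0.2 of the CLI value. "A standard type I error rate (α) of 0.05 and power of 0.8 is desired", and the result is 160 control limbs and 240 PAD limbs, with at least 54 claudication and at least 100 CLI limbs among the latter. The section gives no formula, null value, sidedness, dropout allowance or clustering allowance.

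The analysis is set elsewhere. Under SAP section 7.2 the model value "will be derived by the Research and Development team and will consist of the acceleration time". Protocol section 12.1.2 describes something broader, in which "a combination of the flow amplitude and one or more features of the waveform may be used as inputs to train the predictive model". SAP section 4.1.1.1.1 defines PAD by ABI at or below 0.9 or above 1.4 with TBI at or below 0.7, with symptoms (definition 1) or without (definition 2), or by a positive postexercise test. It defines CLI by rest pain and active wounds with TBI below 0.3. SAP section 7.10.1 sets the success rule: "If the 95% CI of the AUC excludes 0.5 at all time points for PAD or CLI", acceleration time counts as predictive of that endpoint.

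**The concern.** A power figure is only as good as the effect size behind it. Here the effect sizes belong to a model and to disease definitions that the SAP does not use. The margin around the smaller one is also called conservative without reference to how precisely the pilot measured it. If the true AUC of acceleration time under the SAP definitions lies lower, the chance that an interval excludes 0.5 could be well under 0.8. A reader who trusts 0.8 would then over-read an interval that includes 0.5.

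**Working it through.** **Inputs.** From SAP section 6: AUCs 0.67 and 0.80, allowances ±0.05 and ±0.2, limb counts 160/240/54/100, pilot size 100 limbs, pilot sample sizes 84 and 22. From SAP section 7.10.1: a 95% CI against 0.5, read as two-sided. Assumed here: independent limbs and one visit.

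**Bounds.** 0.67 − 0.05 = 0.62 for claudication; 0.80 − 0.20 = 0.60 for CLI.

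**Formulas.** With A the AUC, m cases and n controls:
- Hanley–McNeil: SE² = [A(1−A) + (m−1)(Q1−A²) + (n−1)(Q2−A²)]/(mn), with Q1 = A/(2−A) and Q2 = 2A²/(1+A).
- Binormal (Obuchowski): SE² = 0.0099·exp(−a²/2)·[(5a²+8) + (a²+8)/k]/m, with a = 1.414·Φ⁻¹(A) and k = n/m.
- Power = Φ((A − 0.5)/SE − 1.96).

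**Reproducing the SAP's figure at its own bounds.** For 54 v 160 at 0.62, Q1 = 0.4493, Q2 = 0.4746 and A² = 0.3844. SE² = (0.2356 + 53×0.0649 + 159×0.0902)/8640 = 0.00208, so SE = 0.0457. Power = Φ(0.12/0.0457 − 1.96) = Φ(0.67) = 0.75.

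| Cases v controls | AUC | Hanley–McNeil | Binormal | Simulated DeLong CI |
|---|---|---|---|---|
| 54 v 160 (claudication minimum) | 0.62 | 0.75 | 0.775 | 0.73–0.76 |
| 100 v 160 (CLI minimum) | 0.60 | 0.78 | 0.80 | 0.78 |
| 140 v 160 | 0.62 | 0.96 | 0.96 | 0.95 |
| 240 v 160 (all PAD) | 0.62 | 0.99 | 0.99 | 0.99 |

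The simulation used 6,000 runs per case with normal and with exponential scores. The CLI figure reproduces: the binormal formula returns 100 cases for 160 controls. Claudication needs 59 (binormal) to 64 (Hanley–McNeil) limbs for 0.80. No variant tried leads to 240 PAD limbs.

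**How precise was the pilot?** The case/control split behind 0.67 is not given, so every split with at least five limbs per group was tried.
- 100 limbs: the smallest Hanley–McNeil SE is at 56/44, √[(0.2211 + 55×0.0549 + 43×0.0887)/2464] = 0.0535. Half-width 1.96×0.0535 = 0.105.
- 84 limbs: the smallest SE is at 47/37, 0.0584. Half-width 0.115.
- Uneven splits are worse: 84/16 gives 0.132.

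So ±0.05 is at most 0.05/0.105 = 48% of the half-width for 100 limbs, or 0.05/0.115 = 44% for 84: about one standard error. For CLI at 0.80, the splits tried give half-widths of about 0.12 to 0.23, so ±0.2 covers most of them.

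**Power at the pilot's lower limit.** The best cases are 0.67 − 0.105 = 0.565 and 0.67 − 0.115 = 0.555. Over 0.55–0.57, with both formulas and the variance taken at the assumed or the null AUC:
- 54 v 160: 0.19 to 0.35
- 240 v 160: 0.39 to 0.69

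**Pilot against analysis.**

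| | Pilot | SAP analysis |
|---|---|---|
| Predictor | built diagnostic model, inputs not named | acceleration time alone |
| PAD | ABI below 0.9 | ABI plus TBI, or postexercise test |
| CLI | Rutherford 4 or higher | rest pain and wounds, TBI below 0.3 |

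**The case against.** Several points on the other side stand.

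- A reader might infer from 0.75 that the primary PAD analysis is underpowered. The documents do not support that. The 54 limbs are a minimum within 240, and SAP section 7.10.1 plans no claudication-only ROC. At 0.62, 240 v 160 limbs reach 0.99. The number of limbs meeting each PAD definition is not given, so no shortfall is shown for either.
- The shortfall of 2.5 to 5 points by formula depends on method and sidedness. A one-sided 0.05 test would give 0.84–0.86. Section 6 calls the counts approximate, and the two methods sources it cites were not available here. The two-sided reading comes from the 95% CI in section 7.10.1.
- The CLI arm might be read as short as well. It is not: 0.78–0.80 matches the target.
- 84 + 22 = 106 might look like a contradiction with 100 limbs. The SAP calls these sample sizes for two AUCs, which may share controls. As an illustration, 77 claudication + 15 CLI + 7 shared control limbs make 99 limbs and give 84 and 22. The text is unclear, not shown to be wrong.
- That the predictor differs is an inference. Neither document names the pilot model's inputs. The difference in definitions is explicit.

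The SAP could also reply that section 7.2 calls the objectives not hypothesis-driven. That does not settle the matter, because section 7.10.1 sets a pass/fail rule and section 6 ties the counts to 0.8.

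**Conclusion.** The concern holds in limited form. The 0.8 is not supported for the predictor and definitions that will be analysed, and ±0.05 around 0.67 is not conservative: it is less than half the pilot's 95% half-width for every split of 84 or 100 limbs. That criticism does not extend to ±0.2 for CLI. At the stated bounds, 0.8 is clearly missed only for the 54-limb claudication floor (0.75–0.78 by formula). The main exposure is that power for PAD depends heavily on 0.62: for 240 v 160 limbs it falls from 0.99 to 0.39–0.69 if the AUC is 0.55–0.57.

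These figures assume independent limbs, one visit, a two-sided 95% CI and full limb counts. They lean to the favourable side. The minimum of 250 patients for 400 limbs is 1.6 limbs per patient. With an assumed within-patient correlation of 0.3 to 0.7, the design effect 1 + 0.6ρ is 1.18 to 1.42, and the Hanley–McNeil 0.75 becomes 0.68 to 0.60. Success is also required at all three time points, on complete cases.

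**What to change.** In SAP section 6:

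1. Remove the word conservative for ±0.05, or replace that allowance with the pilot's lower confidence limit.
2. State what 84 and 22 count, with cases and controls for each pilot ROC.
3. State the null AUC, sidedness and variance formula. Give a table of power for each planned ROC (PAD definition 1, PAD definition 2, CLI) with expected limb numbers, at the stated bound and at the pilot lower limit. Use acceleration time from the pilot recordings and the SAP definitions, if those data exist.
4. If they do not, delete the 0.8 claim and give expected CI half-widths. With the Hanley–McNeil SE these are about 1.96×0.0280 = 0.055 for 240 v 160 at 0.62 and 1.96×0.0365 = 0.072 for 100 v 160 at 0.60.

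The cost is a re-analysis of existing pilot data, where available, and new wording in one section. Enrolment and the planned analyses stay as they are. The downside is a less favourable stated power.
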